### 4.2.3. Adherence to Study Drug Regimen

Two measures of study drug regimen adherence will be estimated based on data collected at the site or reported directly by study participants:

- 1) Prescribed (in-study) pill counts based on pill dispensations and returns on the Study Drug Accountability eCRF,
- 2) Self-report from CASI questionnaires

Using a randomly selected cohort of study participants, TFV-DP levels in RBCs from DBS analyses (Appendix 9) are planned in order to provide objective data on drug adherence. TFV-DP levels in RBCs from DBS will be analyzed.

## 4.2.3.1. Adherence to Study Drug Regimen During Study via Pill Counts

For the DB phase, study drug regimen (in-study) prescribed adherence will be computed based on pill counts for active drug only (ie, study drug regimen in Treatment Group 1 includes 1 study drug: *F/TAF active*. Study drug regimen in Treatment Group 2 includes 1 study drug: *F/TDF active*. The numbers of pills of study drug dispensed and returned are captured on the Study Drug Accountability eCRF.

The level of prescribed adherence (or in-study adherence) to the study drug regimen will be determined by the total amount of study drug administered relative to the expected total amount of study drug (1 pill per day for the duration of study participation based on the protocol) and will be calculated from first study drug start date to the end date defined as the latest of the study drug start dates and end dates, the clinic visit dates, and the laboratory visit dates during the DB phase, excluding the 30-day follow-up visit date. If the subject has been diagnosed with HIV infection during the DB phase, the later date of either the 1) HIV diagnosis date or 2) the DB phase last dose date will be used as the end date. Per study design, subjects that have been diagnosed with HIV infection must immediately discontinue study drug but may remain in the study.

The level of prescribed adherence will be expressed as a percentage using the following formula:

$$Prescribed\ Adherence\ (\%) = \frac{Total\ Amount\ of\ Study\ Drug\ Administered}{Total\ Amount\ of\ Study\ Drug\ Expected\ While\ Participating\ in\ Study} \times 100$$

- [1] Total amount of study drug administered is the number of pills dispensed minus the number of pills returned.
- [2] Total amount of study drug expected while participating in the study is calculated as the daily number of pills prescribed for the study drug multiplied by the duration of study participation defined as from first dose date to the end date defined as the latest of the study drug start dates and end dates, the clinic visit dates, and the laboratory visit dates excluding the 30 day follow up visit date. If the subject has been diagnosed with HIV infection, the later date of either the 1) HIV diagnosis date or 2) last dose date will be used as the end date.

If any study drug bottle was not returned, the bottle return status was unknown or the number of pills returned was missing, then it is assumed the number of pills returned was zero. The number of pills taken after the last bottle dispensation visit will be the minimum of 1) the number of pills dispensed minus the number of pills returned (if some bottles were returned) or 2) the number of days between the last bottle dispensation date to the end date as defined in this section. Each subject's adherence rate will be capped at 100%.

Descriptive statistics for overall prescribed adherence (n, mean, SD, median, Q1, Q3, minimum, and maximum) along with the number and percentage of subjects belonging to adherence categories (ie, < 30%,  $\ge 30\%$  to < 60%,  $\ge 60\%$  to < 80%,  $\ge 80\%$  to < 90%,  $\ge 90\%$  to < 95%,  $\ge 95\%$ ) will be provided by treatment group and overall for subjects in the Safety Analysis Set. No inferential statistics will be provided.

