- If the HBsAg or HBV DNA result is positive, the participant will be discontinued and referred to appropriate HBV treatment. If the participant has acquired HIV, they may continue participation in the study at the discretion of the investigator.

— Hepatitis C testing (**every 48 weeks**)

- If the HCV Ab result is positive, then HCV RNA will be completed unless there is documented evidence that sustained virologic response has been achieved. If the HCV RNA result is positive, the participant may continue in the study at the discretion of the investigator.
- Participants who have tested positive for HCV Ab on the study during a prior visit do not need to repeat the HCV Ab test during subsequent visits and instead will have HCV RNA testing performed at visits every 48 weeks

CC

CCU [REDACTED]

CCU [REDACTED]

- Plasma sample storage for virology, safety, and/or PK testing
- CD4, CD8, and CD4/CD8 ratio (**only for participants who acquire HIV**)
- Large volume blood draw for the following (only for participants who acquire HIV. All blood draws will be done at the first study visit upon confirmation of HIV infection, and at the additional timepoints as indicated below. Subsequent draws will be performed at the participants' regularly scheduled study visit):
 - Latent and Active Reservoir assessment (24 weeks and 48 weeks after HIV infection, and every 48 weeks thereafter)
 - T cell response and phenotype (24 weeks and 48 weeks after HIV infection, and every 48 weeks thereafter)
 - Viral Sequence Diversity assessment (**24 weeks after HIV infection only**)
- Inflammatory/immune activation biomarkers (only for participants who acquire HIV. Done at the first study visit upon confirmation of HIV infection, at 24 weeks and 48 weeks after HIV infection, and every 48 weeks thereafter)
- CASI for sexual risk events and adherence since the last visit
- Collect and review used and unused blinded study drug for accountability and calculate compliance (**not done for participants who have permanently discontinued study drug**)
- Drug dispensation (not done for participants who have been or will be permanently discontinued from study drug)

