6.9. Criteria for Discontinuation of Study Treatment

If a participant discontinues study dosing (for example, as a result of an AE), every attempt should be made to keep the participant in the study and continue to perform the required study-related follow up and procedures until the end of blinded treatment phase visit. If this is not possible or acceptable to the participant or investigator, the participant may be withdrawn from the study.

Study medication will be discontinued as applicable in the following instances:

- HIV-1 infection is confirmed
- Unacceptable toxicity, or toxicity that, in the judgment of the investigator, compromises the ability to continue study-specific procedures or is considered to not be in the participant's best interest
- Participant request to discontinue for any reason

Study medication may be discontinued as applicable in the following instances:

- Intercurrent illness that would, in the judgment of the investigator, affect assessments of clinical status to a significant degree. Following resolution of intercurrent illness, the participant may resume study dosing at the discretion of the investigator (see Section 6.8 for criteria for restarting study drug after an interruption).
- Participant noncompliance
- Discontinuation of the study at the request of Gilead, a regulatory agency or an institutional review board (IRB) or independent ethics committee (IEC)

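### For people who stop study drug for reasons other than HIV infection but stay in blinded follow-up, the pill-count adherence score depends on retention, not on pill-taking while on drug

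*SAP*

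**What the plan says.** SAP 4.2.3 names two participant-level adherence measures, an in-study pill count and self-report from the CASI questionnaire. Drug levels from dried blood spots are planned in a randomly selected cohort.

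For the pill count (SAP 4.2.3.1):

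- Numerator: "Total amount of study drug administered is the number of pills dispensed minus the number of pills returned".
- Denominator: "1 pill per day for the duration of study participation based on the protocol", counted from first dose to an end date.
- End date in general: "the latest of the study drug start dates and end dates, the clinic visit dates, and the laboratory visit dates" in the blinded phase, leaving out the 30-day follow-up visit. Nothing ends the count at the last dose.
- End date after an HIV diagnosis: "the later date of either the 1) HIV diagnosis date or 2) the DB phase last dose date will be used as the end date". The reason given is that these participants "must immediately discontinue study drug but may remain in the study".

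Each rate is capped at 100% and summarised by arm in the Safety Analysis Set, as descriptive statistics and in categories from under 30% to at least 95%. No inferential statistics are planned. Footnote [2] repeats the end-date rule. Appendix 12 item 19 does not change it for people who stay.

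On follow-up, Protocol 3.2 lets participants remain in the blinded phase off drug. Protocol 6.9 says that after a stop "every attempt should be made to keep the participant in the study and continue to perform the required study-related follow up". Protocol 6.7.1 asks for the ESDD visit within 72 hours of stopping drug.

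**The concern.** Once a participant has permanently stopped, no more drug is dispensed, yet the denominator adds one expected pill for each day up to the last blinded-phase visit. Two people with the same pill-taking can therefore land at opposite ends of the category table, according only to whether they agreed to stay. The participants who do what the protocol asks after a stop get the low score.

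The SAP's reason for cutting the count at HIV diagnosis applies to other stops as well. Protocol 5.1, for example, has drug discontinued after unblinding to the investigator and follow-up continued. The neighbouring measures do stop: exposure (SAP 4.2.1) ends at last dose, and self-report adherence (SAP 4.2.3.2) ends with the visit window of permanent discontinuation.

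The pill count is the only measure not based on self-report that covers the whole Safety Analysis Set, since the dried blood spot cohort is about 10% of participants. It is shown by arm. If permanent stops, or willingness to stay after a stop, differed between F/TAF and F/TDF, the table would show an adherence difference that need not exist.

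**Working it through.** The documents report no pill-count result, so there is no figure to reproduce. The check applies the SAP formula to a participant without HIV infection who takes every pill until a permanent stop and returns all unused pills.

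**Inputs.** One pill per day, end date and 100% cap from SAP 4.2.3.1. Blinded phase of at least 96 weeks, or 672 days (SAP 1.2). ESDD visit 0 to 3 days after last dose (Protocol 6.7.1).

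**Formula.** Adherence = (pills dispensed − pills returned) / (days from first dose to end date), capped at 100%. For a stayer the end date is the last blinded-phase visit. For a leaver it is the ESDD visit.

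| Permanent stop | Stays to Week 96 | Leaves at ESDD visit |
|---|---|---|
| Week 12 (84 days) | 84/672 = 12.5% | 100% down to 84/87 = 96.6% |
| Week 24 (168 days) | 168/672 = 25.0% | 100% down to 168/171 = 98.2% |
| Week 48 (336 days) | 336/672 = 50.0% | 100% down to 336/339 = 99.1% |
| Week 72 (504 days) | 504/672 = 75.0% | 100% down to 504/507 = 99.4% |

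The Week 24 stopper falls in the under-30% category by staying and in the at-least-95% category by leaving. Longer follow-up widens the gap: to Week 120 the stayer scores 168/840 = 20.0%.

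**Limits of the contrast.** A leaver who stops at Week 4 may score 28/31 = 90.3%, below the top category. A stayer who stops after about Day 638 (0.95 × 672) still scores at least 95%. Unreturned bottles count as taken, so a Week 24 stopper who keeps 90 pills (assumed: three 30-tablet bottles) scores (168 + 90)/672 = 38.4%.

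**Effect on an arm.** This needs a share s of the arm that stops for reasons other than HIV and stays to Week 96. The documents do not give it. Assume s of 2%, 5% or 10%, stop days uniform from 28 to 671, and perfect pill-taking otherwise.

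- Mean score of stayers: ((28 + 671)/2)/672 = 349.5/672 = 0.520.
- Fall in arm mean, s × (1 − 0.520): 1.0, 2.4 and 4.8 points.
- Stayers scoring under 80%: stops before Day 537.6, which is 510 of 644 possible days, or 0.792. As a share of the arm: 1.6%, 4.0% and 7.9%.

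If s were 10% in one arm and 5% in the other, the means would differ by 4.8 − 2.4 = 2.4 points with identical adherence on drug.

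**After the change.** With both counts ended at last dose, stayer and leaver in every row of the table score 100%.

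**The case against.** The strongest reply is that this is a labelled definition, not a mistake. The SAP calls the measure in-study, defines its denominator by study participation, and follows it with a self-report measure explicitly restricted to on-treatment time. The HIV exception also coincides with the end of at-risk time in SAP 6.2.3. It stands that nothing here is an arithmetic error. But the label does not cure the problem. A true coverage measure would score every early stopper low, whereas this one scores those who leave near 100% and those who stay far lower.

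It also stands that the consequence is limited. The summary is descriptive. SAP 6.3 drops the adherence criterion from the per-protocol set, and adherence neither defines the Full Analysis Set nor enters the rate-ratio model.

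Four stronger readings are tempting, and the documents do not support them.

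- That the protocol forbids calculating compliance for anyone who has stopped. The line in Protocol 6.3, "not done for participants who have permanently discontinued study drug", concerns scheduled visits after the stop. Protocol 6.7.1 has compliance calculated at the ESDD visit. Neither sets an analysis denominator, and the SAP's reference to the protocol may qualify only the one pill per day.
- That hepatitis B stops are a clear example of stopping drug and staying. Protocol 6.3 says such participants are discontinued, and mentions continued participation only for those who have acquired HIV.
- That a stopper who returns no bottles is credited with a pill for every day to the last visit. With last dispensing at Day 84 and a last visit at Day 840, that would be (84 + 756)/840 = 100%. It rests on one parenthesis in the last-interval rule. The same paragraph sets pills returned to zero when a bottle is not returned, and footnote [1] defines drug administered as dispensed minus returned. Credit is then limited to pills dispensed: with 90 pills, (84 + 90)/840 = 21%. At most the wording is loose.
- That the arms will differ. The documents show no difference between arms in stopping or staying.

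**Conclusion.** The point holds for participants who permanently stop drug for reasons other than HIV infection and remain in blinded follow-up. For them the pill count mixes adherence with retention. At individual level this follows from the SAP's own formula and can move a perfect pill-taker from the top category to the bottom one. At arm level the size is not known: a fall of about 1 to 5 points rests on an assumed 2% to 10% stopping and staying, with uniform stop times.

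A reader might infer that the in-study figure must be replaced as the main pill-count result. The documents do not require that. The measure is labelled in advance and is descriptive, and the study had already been unblinded for the primary analysis when this SAP was written. An added summary is enough. This is a cheap improvement to a descriptive by-arm table and does not threaten the trial's efficacy conclusions.

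**What to change.** Add to SAP 4.2.3.1 an on-treatment pill-count adherence summary by arm, with the same categories. For every permanent discontinuation, end both pills taken and pills expected at the blinded-phase last dose date defined in SAP 3.8.1. Use this summary to describe adherence while on drug.

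Keep the existing figure for comparability with the primary report (the SAP for that report is not among the documents, so a matching definition is assumed). Label it as in-study coverage that is affected by retention after a stop.

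The cost is one end date in a program, a few lines of text and one extra table. Early stoppers will not lower the added figure, but their lost coverage is already shown in disposition (SAP 4.1.2) and in time to discontinuation (SAP 4.2.1). No efficacy analysis changes.

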### 4.2.3.2. Adherence to Study Drug Regimen While On-Treatment via Self Report

For the DB phase, adherence to study drug while on-treatment via patient self-report from the CASI follow-up questionnaire data will be summarized by visit from the question: "Approximately how many doses (days) of PrEP tablets have you missed since your last study visit?"

Adherence rates will be calculated based on the number of pills taken divided by the number of days between visits. The number of pills taken is the number of days between visits minus the number of doses (days) of PrEP tablets missed. The number of days between visits is based on 28 days between Day 1 and Week 4, 56 days between Week 4 and Week 12 and 84 days between

visits starting on Week 24 and later. Each subject and visit combinations' minimum adherence rate will be capped at 0%. On-treatment data includes visits occurring through the upper limit of the analysis window corresponding to the date of permanent discontinuation of study drug for subjects that permanently discontinued study drug or all available postbaseline data for subjects who were still on study drug.

By visit descriptive statistics for the adherence rate based on the number of pills missed (n, mean, SD, median, Q1, Q3, minimum, and maximum) along with the number and percentage of subjects in adherence categories based on missing the following number of pills (or days) will be summarized.

Table 4-1. Adherence Rates from Number of Doses (Days) of PrEP Tablets Missed in CASI

Adherence rate approximation	Week 4	Week 12	Week 24 and later visits
< 30% adherence	≥ 20 days	≥ 40 days	≥ 59 days
≥ 30% to < 60% adherence	≥ 12 to ≤ 19 days	$\geq$ 23 days to $\leq$ 39 days	$\geq$ 34 days to $\leq$ 58 days
≥ 60% to < 80% adherence	≥ 6 to ≤ 11 days	$\geq$ 12 days to $\leq$ 22 days	$\geq$ 17 days to $\leq$ 33 days
≥ 80% to < 90% adherence	$\geq 3$ to $\leq 5$ days	≥ 6 to ≤ 11 days	≥ 9 to ≤ 16 days
≥ 90% to < 95% adherence	2 days	$\geq$ 3 to $\leq$ 5 days	$\geq$ 5 to $\leq$ 8 days
≥ 95% adherence	≤ 1 day	≤ 2 days	≤ 4 days

Approximate adherence rates are based on 28 pills prescribed for 28 days between Day 1 and Week 4, 56 pills prescribed for 56 days between Week 4 and Week 12 and 84 pills prescribed for 84 days between visits starting on Week 24 and later.

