From the time of obtaining informed consent through the first administration of study drug, record all SAEs, as well as any AEs related to protocol-mandated procedures on the adverse events electronic case report form (eCRF). All other untoward medical occurrences observed during the screening period, including exacerbation or changes in medical history are to be captured on the medical history eCRF. See Section 7 Adverse Events and Toxicity Management for additional details.

6.3. Treatment Assessments Blinded Phase (Weeks 4, 12, and Every 12 Weeks Until the end of blinded treatment phase visit)

The following evaluations are to be completed at the Weeks 4, 12, and every 12 weeks visits until the end of blinded treatment phase visit unless otherwise specified.

All study visits are to be scheduled relative to the Day 1 visit date. Study visits are to be completed within ± 2 days of the protocol-specified visit date based on the Day 1 visit through Week 12 and study visits thereafter completed within ± 14 days of the protocol-specified visit date through the end of blinded treatment phase visit, unless otherwise specified.

Regularly scheduled evaluations will be performed for all participants whether or not they continue to receive study drug, unless otherwise specified.

- Targeted (symptom directed) physical examination (complete physical examination at Weeks 48 and 96 only)
- Review of AEs and changes in concomitant medications, including assessment of whether any STIs were diagnosed and any treatments were received since last visit
- When clinically indicated, vital signs measurement (blood pressure, pulse, respiration rate, and temperature)

- Weight
- STI testing. Participants who test positive for any STI will be treated in accordance with local STI guidelines.
 - Genital, rectal, and pharyngeal examination as appropriate
 - Pharyngeal and rectal swabs for gonorrhea and chlamydia (per local lab). Swabs may be self-administered by the participant at the discretion of the investigator (rectal swab not required at Week 4).
 - Urine sample for gonorrhea and chlamydia (per central lab)
 - Blood sample for syphilis testing (per local lab)
- Fourth generation rapid HIV-1 Ab/Ag or third generation rapid HIV-1 Ab test (**not done for HIV-infected participants**)

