## • For postbaseline visits:

For BMD data, the record(s) collected on the latest day in the window will be selected for analysis.

For CASI Follow-Up questionnaires, the record(s) collected on the day closest to the nominal day for that visit will be selected. If there are 2 days equidistant from the nominal day, the later day will be selected. Additionally, as some subjects retrospectively completed CASI questionnaires for previous missed visits, when multiple record(s) occur on the same day, the record with a subject assigned visit week equal to the analysis window visit week defined in Section 3.8.2 will be selected.

For Week 4 PK and PBMC trough samples, analysis windows will not be applied, but only samples labeled as a 'trough' collection will be selected. For anytime PK samples, only samples labeled as an 'anytime' collection will be selected and the rules below for other numeric observations applied.

For other numeric observations (ie, except BMD, CASI and Week 4 trough specified above), the record(s) collected on the day closest to the nominal day for that visit will be selected. If there are 2 days equidistant from the nominal day, the later day will be selected.

For any numeric observations, if there are multiple records on the selected day, the average will be taken.

If multiple valid nonmissing categorical measurements exist in a window, records will be chosen as follows:

- For baseline, the last available record on or prior to the first dose date of study drug will be selected. If there are multiple records with the same time or no time recorded on the same day, the value with the lowest severity will be selected (ie, normal will be selected over abnormal) except for gonorrhea and chlamydia laboratory STIs where the worst severity value will be selected (ie, abnormal will be selected over normal).
- For postbaseline visits, the worst severity value within the window will be selected (ie, abnormal will be selected over normal).

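### SAP 4.2.3.2 divides doses missed since the last actual visit by a nominal 28, 56 or 84 days, so self-reported adherence is biased for participants who missed doses and whose visits were not on the nominal day

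*SAP*

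**What the plan says.** Adherence by self-report comes from one CASI follow-up item: "Approximately how many doses (days) of PrEP tablets have you missed since your last study visit" (SAP 4.2.3.2). The rate is defined in two steps: "Adherence rates will be calculated based on the number of pills taken divided by the number of days between visits", and "The number of pills taken is the number of days between visits minus the number of doses (days) of PrEP tablets missed". The days between visits are then set by visit, not taken from dates: "The number of days between visits is based on 28 days between Day 1 and Week 4, 56 days between Week 4 and Week 12", with the Table 4-1 footnote giving "84 pills prescribed for 84 days between visits starting on Week 24 and later". There is a floor: "minimum adherence rate will be capped at 0" percent. Table 4-1 turns fixed counts of missed days into six adherence bands and labels them approximations.

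Visit timing is in protocol 6.3: "Study visits are to be completed within ± 2 days of the protocol-specified visit date based on the Day 1 visit through Week 12", and ±14 days after that, all relative to Day 1. CASI is also completed at the early study drug discontinuation visit (protocol 6.7.1) and at the end of blinded treatment phase visit, which may or may not coincide with a scheduled visit (protocol 6.4).

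SAP 3.8.3 adds a rule for same-day CASI records, "as some subjects retrospectively completed CASI questionnaires for previous missed visits": the record whose assigned week matches the analysis window is kept. Neither that rule nor Appendix 12 item 21 replaces the nominal interval with actual days.

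**The concern.** The count of missed doses covers the time that actually passed since the last visit. The denominator covers the time that should have passed. When the two differ, the ratio is not an adherence rate for either period: a short interval leaves too few days in which doses could be missed, so adherence is overstated, and a long interval does the reverse. Because the Table 4-1 bands are fixed missed-day counts, the same mismatch carries into the band counts at each visit.

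At stake is the accuracy of the by-visit self-report adherence table. The SAP handles its other site-based measure differently: pill-count adherence in 4.2.3.1 runs from first dose to an actual end date. CASI records are dated too, since 3.8.2 and 3.8.3 assign them to windows by day.

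**Working it through.** **Inputs.** D = 28, 56 or 84 days (SAP 4.2.3.2); m = doses reported missed; T = actual days since the last visit; f = m/T. Visit windows are from protocol 6.3.

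**Step 1: reproduce Table 4-1.** SAP rate = max(0, (D − m)/D). Adherence is below a cut-off c when m > D(1 − c). For c = 30, 60, 80, 90 and 95%:

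- D = 84: 58.8, 33.6, 16.8, 8.4, 4.2, so the bands start at 59, 34, 17, 9 and 5 missed days.
- D = 56: 39.2, 22.4, 11.2, 5.6, 2.8, so 40, 23, 12, 6 and 3.
- D = 28: 19.6, 11.2, 5.6, 2.8, 1.4, so 20, 12, 6, 3 and 2.

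All 18 cells of the table are reproduced. The cut-offs are right for the nominal intervals, and they confirm that nominal intervals are used.

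**Step 2: intervals possible within protocol windows.**

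- Day 1 to Week 4: 28 ± 2 = 26 to 30 days.
- Week 4 to Week 12: 56 ± 4 = 52 to 60 days.
- Week 12 to Week 24: (168 − 14) − (84 + 2) = 68 to (168 + 14) − (84 − 2) = 100 days.
- Consecutive visits from Week 24 on: 84 ± 28 = 56 to 112 days.

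**Step 3: size of the error.** The SAP value is 1 − fT/D and the true value is 1 − f, so before the floor the error is f(1 − T/D). It is zero when f = 0 or T = D, positive for short intervals and negative for long ones.

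**Step 4: cases.**

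| Actual days T | Missed m | D | SAP rate | True rate | SAP band | True band |
|---|---|---|---|---|---|---|
| 56 | 56 | 84 | 28/84 = 33.3% | 0% | 30 to <60 | <30 |
| 56 | 28 | 84 | 56/84 = 66.7% | 50% | 60 to <80 | 30 to <60 |
| 112 | 56 | 84 | 28/84 = 33.3% | 50% | 30 to <60 | 30 to <60 |
| 112 | 84 | 84 | 0/84 = 0% | 25% | <30 | <30 |
| 112 | 11 | 84 | 73/84 = 86.9% | 101/112 = 90.2% | 80 to <90 | 90 to <95 |
| 68 (Week 12 to 24) | 68 | 84 | 16/84 = 19.0% | 0% | <30 | <30 |
| 60 (Week 4 to 12) | 30 | 56 | 26/56 = 46.4% | 50% | 30 to <60 | 30 to <60 |
| 30 (Day 1 to Week 4) | 15 | 28 | 13/28 = 46.4% | 50% | 30 to <60 | 30 to <60 |
| any | 0 | any | 100% | 100% | ≥95 | ≥95 |

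**Step 5: visits outside the 12-week pattern.** Suppose the last visit was on day 168 and a discontinuation visit falls on day 218. That is in the Week 36 window (days 211 to 294, SAP Table 3-1), so D = 84 while T = 50. With 25 of 50 doses missed, and if this is the record kept for the window, the SAP gives 59/84 = 70.2% against a true 50%. No protocol window is breached.

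**The case against.** The SAP does not hide what it is doing. The question asks for an approximate number, and the table and its footnote call the rates approximations. The 33% for someone who took nothing needs one visit 14 days late, the next 14 days early, and no doses at all. Visits are anchored to Day 1, so in-window shifts do not accumulate and a long interval tends to be followed by a shorter one. At 90% adherence a single 14-day shift gives 1 − 0.1 × 98/84 = 88.3% or 1 − 0.1 × 70/84 = 91.7%. All of this stands, and it limits the importance of the point. It does not remove the mismatch: the label warns of imprecision, not that numerator and denominator cover different periods.

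The obvious repair can also go wrong. If a questionnaire completed late for a missed visit covers 84 days with 42 doses missed, true adherence is 50% and the SAP gives 50%. Dividing by 168 days to the completion date gives (168 − 42)/168 = 75%. This stands too, and retrospective records need their own rule.

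A reader might infer more than the documents support:

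- *That someone who took half after a missed visit is reported at 0%.* The arithmetic, (84 − 84)/84, is right only if one answer covers the whole 168-day gap. Some participants filled in the missed questionnaire later, and the SAP does not say what period such an answer covers.
- *That irregular attenders are the least adherent, so the error falls where it matters most.* Nothing in either document shows this.
- *That the 0% floor exists only because of the fixed denominator.* Approximate recall can exceed the true interval as well, so a floor is useful either way.
- *That efficacy results are affected.* SAP 6.3 drops adherence from the per-protocol definition, and the case-control analysis of adherence and infection in Appendix 9 uses dried-blood-spot bands, not CASI.

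**Conclusion.** The mismatch is real and worth correcting, but its reach is narrow. For in-window visits from Week 24 on, the reported rate can be up to 33 percentage points too high (nothing taken over 56 days) and, allowing for the floor, up to 25 points too low (a quarter taken over 112 days). At 90% adherence the in-window extremes are about ±3.3 points (0.1 × 28/84), which can still cross a band boundary. Within the ±2-day windows at Weeks 4 and 12, half-taken adherence moves by at most 3.6 points downward.

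These figures assume that participants answer the question as worded, for the time since the last attended visit. The documents give no distribution of visit intervals and no count of missed visits, so neither the number of affected records nor the effect on any mean or band count can be computed.

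Only the by-visit self-report summaries are touched. Appendix 12 item 11(j) mentions adherence rate as an example of an ordinal variable for a row mean score test, so a p-value on the bands cannot be ruled out, but that would not be an efficacy or safety conclusion. The same rule applies in both arms, and nothing in the documents suggests that visit timing differs between them.

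**What to change.** In SAP 4.2.3.2:

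1. For a questionnaire completed at the visit it refers to, use as denominator the actual days from the previous attended visit (or from first dose, for the first questionnaire) to that visit. Apply this to discontinuation and end of blinded treatment phase visits as well.
2. Keep the 0% floor.
3. Derive the six bands from the resulting percentage instead of the fixed missed-day counts in Table 4-1.
4. For a questionnaire completed retrospectively for a missed visit, state the period the answer covers and use that period, or keep the nominal interval. Do not use the completion date. Set the interval for the next questionnaire so that the two periods do not overlap.

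The cost is a small programming change and one extra rule for retrospective records. Items 1 to 3 need no new data. Item 4 needs a decision on the recall period, which the documents do not record.
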